6.3.6 Removal of participants

Stopping Rules

Discontinuation of participants:

Participants for whom there has been at least 2 weeks without participant contact will be discontinued from the study. Exceptions may be made after discussions with the PIs, approval by the Medical Monitor, and consistency with the regulations of the Institutional Review Board/Ethics Committee (IRB/EC).

Discontinuation of study:

The study will be stopped if, in the judgment of the DSMB or the PI, there are sufficient safety concerns that arise during the conduct of the study that would indicate that participants are being harmed by the study interventions. Examples of such safety concerns would be:

-Other events that pose unacceptable risks to participants, e.g., multiple SAEs that are judged to be related to study interventions.

Withdrawal Rules

Discontinuation of Participants:

If a participant who does not meet enrollment criteria is enrolled, the study sponsor will be contacted. In such cases, the PI will provide information on the participant's anticipated benefit or current benefit from being enrolled in the study or continuing to receive study drug respectively. In addition, the PI will discontinue participants from the study drug or the study or both in the following circumstances:

- Participant has evidence of progressive disease.
- The participant, for any reason, requires treatment with another therapeutic agent that has been demonstrated to be effective for treatment of the study indication. In this case, discontinuation from the study occurs prior to introduction of the new agent.
- The PI decides that the participant should be withdrawn from the study. If a SAE or a clinically significant laboratory value is the basis for this decision, the PI will discontinue the study therapy and take appropriate measures. The PI will immediately notify the study sponsor or its designee.
- The participant or attending physician requests withdrawal of the participant from the study.
- The investigator or the study sponsor stops the study or stops the participant's participation in the study for medical, safety, regulatory, or other reasons consistent with applicable laws, regulations, and good clinical practice (GCP).
- The study therapies have shown unacceptable toxicity.
- The participant is noncompliant with study procedures.
- In the clinical judgment of the investigator, the participant requires acute detoxification from the alcohol.
- In the clinical judgment of the investigator, the participant's clinical condition worsens substantially (for example, if weekly alcohol use increases 25% or more over baseline) and it is felt to be in the participant's best interest to obtain alternative treatment including, but not limited to, additionally psychotherapy, pharmacotherapy, hospitalization, etc.

When a participant withdraws before completing the study, the reason for withdrawal will be documented in the CRF and in the source document.

6.4 Statistical Method

Descriptive statistics will be used to summarize the data set. Measures of central tendency and measures of variability will be reported for the chief variables of interest as noted below in 6.4.3.

6.4.1 Statistical Design

As this is a pilot feasibility study, no inferential statistics will be used.

6.4.2 Sample Size Considerations

Not applicable.

6.4.3 Planned Analyses

Descriptive statistics will be used to describe the data set. Measures of central tendency and measures of variability will be reported. Chief variables of interest are listed below in 6.4.3.1, 6.4.3.2, and 6.4.3.3.

6.4.3.1 Primary Analyses

Primary analyses will consist of descriptive statistics. These measures of feasibility are:

1. Time needed to recruit, screen, and run the study procedures for 4 participants
2. Retention rates at the various timepoints in the study process (screening, Human Lab ADP session 1,2,3, and follow-up).
3. Adverse effects of study medication (lacosamide at 2 doses and placebo), before and after alcohol self-administration.

6.4.3.2 Secondary Objectives Analyses

Descriptive statistics will be used to summarize the data set. The variables analyzed will include:

1. Alcohol craving
2. Alcohol consumption during each of the 3 Human Lab ADP sessions.
3. Alcohol – medication interaction effects on BAES, DVT, MD gait and body sway check, Alertness VAS and computer tasks (AAT, BART, and DD)

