3.3.2 Potential Risks and Procedures to Minimize Risks

The major potential risks in this study are related to administration of alcohol, lacosamide, and blood drawing during the physical exam and the alcohol drinking period, and risks to privacy.

Alcohol

A number of medical conditions could potentially be worsened by acute alcohol administration (e.g., liver disease, cardiac abnormality, pancreatitis, diabetes, neurological problems, diabetes, and gastrointestinal disorders). During screening, the study physician will conduct a medical history and physical exam and review laboratory findings. As a result, participants with medical problems that are judged by the study physician/PI ([name]) will be excluded from the study.

Alcohol may also cause nausea in high doses; however, nausea is not expected at the dose being used in this sample of heavy drinkers. Participants will not be drinking to levels more than they typically consume in their own drinking context, and, with the exception of the priming dose, they determine the amount of alcohol consumed.

Another area of potential risk to participants under the influence of alcohol involves their safety during the experimental procedures. Although impairment of gross motor coordination in heavy drinkers is rare at the alcohol dose used in this study, all participants will be under the supervision of the experimenters to prevent possible accidents such as falls. Participants will not leave the laboratory during the self-administration procedure,

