Lacosamide is schedule V controlled substance, indicating a potential for human abuse that is the lowest among the 5 schedules of controlled substances. In a human abuse potential study, single doses of 200 mg and 800 mg of Lacosamide produced euphoria-type subjective responses¹³. At therapeutic doses, the rate of euphoria reported as an adverse effect was less than 1%¹³. No withdrawal syndromes have been reported.

Interactions of Lacosamide and Alcohol

There are no published reports of lacosamide-alcohol pharmacokinetic (PK) or pharmacodynamics interactions. It is reasonable to assume that there may be additive effects of the combination of lacosamide 100mg with alcohol. Possible risks may include added sedation and added psychomotor impairment that could persist for several hours after last alcohol self-administration (2:00-3:00 PM). It is expected that alcohol effects will wear off in the ensuing 5 hours before discharge from the CRC at 8:00 PM. Tests of alertness and gait/body sway will be administered throughout the testing day to monitor these effects.

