4.2 Primary Objective

As this is a small pilot study, the Primary Aims are *process*- rather than *outcome*-oriented:

1. To establish the feasibility and safety of giving lacosamide to human participants in a laboratory alcohol self-administration procedure; and
2. To allow our research team to gain experience with these procedures and fine-tune them.

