5. STUDY DESIGN

5.1 General Design

We will conduct a double-blind, placebo-controlled, within-subjects pilot laboratory trial. Four heavy-drinking, non-treatment seeking community volunteers with AUD will each undergo 3 ADP human laboratory sessions. They will be randomly assigned to receive a single dose of either 1) lacosamide 100 mg, 2) lacosamide 200 mg, or 3) placebo, in a balanced crossover design, in each of 3 human laboratory sessions, with 1 week between sessions. In each session, 2 hours after medication administration, participants will undergo a series of tests (impulsivity, craving, alcohol approach-avoidance task, and as a control measure, a reaction time task (the *Digit Vigilance Test*), followed by a priming drink and two alcohol self-administration periods, using the ADP.

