- **Timeline Followback (TLFB):** at study entry, then Human Lab Session 1, 2 and 3; phone visits 1, 2 and 3. TLFB will be used to calculate standard drinks consumed per week in the past 30 days prior to consent and at the two Human Lab Sessions, and the 1-week follow-up. The TLFB will be used to determine whether subjects meet minimum alcohol consumption criteria at entry. Other substance use will also be collected by TLFB.
- **Balloon Analogue Risk Task (BART):** at each Human Lab session after medication
- **Delay Discounting:** at each Human Lab session after medication

At Follow-up visit:

- **Medical Management:** at the follow-up visit, research clinician will provide a motivational enhancement session to encourage the non-treatment seeking participants to consider treatment.

Measures of Alcohol Effects:

- **Breath alcohol concentration (BrAlc) [99] *at each visit, and multiple times in ADP Sessions 1 and 2.*** BrAlc will be measured at each session to detect recent alcohol use with the *Intoximeters Alco-Sensor IV* instrument.
- **Blood Alcohol Levels:** Human Lab Sessions 1 and 2 (Table 1): Blood samples will be drawn to measure plasma levels of blood alcohol (BAC) during the priming dose and during the alcohol self-administration paradigm. Blood samples will be stored at -4°C and will be analyzed at the San Francisco VA.
- **Biphasic Alcohol Effects Scale (BAES) [81]:** Human Lab Sessions 1 and 2 (Table 1). This 14-item self-report rating scale measures alcohol stimulant/ sedative effects and is used regularly in the Yale ADP.
- **Alcohol Urge Questionnaire (AUQ):** At study entry; multiple times in Human Lab Sessions 1 and 2 (Table 1); 1-wk FU; 1-mo FU: The AUQ is an 8-item questionnaire assessing *desire, expectation of positive effect, and inability to avoid drinking if alcohol is available.* The AUQ is a reliable and valid scale for the measurement of self-reported alcohol urges. Its brevity and time frame for ratings (i.e. right now) makes it suitable for the ADP.
- **Yale Craving Scale -Short (YCS):** Multiple times in Human Lab Sessions 1 and 2; visual analog scale that measures craving for alcohol

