- **Ratings of Drinking Behavior During the Alcohol Self-Administration Period:** multiple times in Human Lab Sessions 1 and 2. Subjects will be videotaped during the alcohol self-administration portion of ADP 1 and ADP 2. Videotapes will be rated by two independent for the onset and offset of each sip of alcohol. Dependent measures will be constructed including time until the first sip and average time to consume each drink.
- **Vital Signs:** Human Lab Sessions 1 and 2 (Table 1). These will include heart rate, blood pressure, and skin. The blood pressure cuff will be on subject's dominant arm while the probe of will be attached to the middle finger of the subject's non-dominant arm. These data will be further used to examine the safety of using the study medications during alcohol self-administration.

Participant Incentives

STUDY VISIT	REIMBURSEMENT AMOUNT
Screening/baseline	\$85*
ADP Lab Session 1	\$224**
ADP Lab Session 2	\$224**
ADP Lab Session 3	\$224**

Follow-up visit	\$25
Bonus for completing ADP Sessions 1 + 2 + 3	\$50
Total	\$832

*At the screening/baseline visit, participants are paid per task they complete. At the end of screening, they will earn \$85.

**Participants will receive \$200 for each ADP Lab Session they complete. They could earn an additional \$24 per ADP Lab Session, depending on how many drinks they consume per session. At each session, participants are offered 8 drinks, each worth \$3. They will receive \$3 per drink for every drink that is not consumed.

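### Section 6.3.5 gives two lab sessions for measures that the rest of the plan takes in three; separately, the interaction summary does not set impairment readings beside alcohol exposure

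*Combined protocol and SAP*

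**What the plan says.** Section 5.1 describes three sessions per man, one for each condition. In each, a battery of tests two hours after dosing is "followed by a priming drink and two alcohol self-administration periods, using the ADP". Section 6.3.5 then gives the timing of the measures in two places:

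- The visit table lists breath alcohol, blood alcohol, vital signs, AUQ, BAES, YCS and drinking-behaviour ratings under all three lab sessions.
- The measure descriptions below it name two sessions. For blood alcohol: "Human Lab Sessions 1 and 2 (Table 1): Blood samples will be drawn to measure plasma levels of blood alcohol (BAC". For BAES: "Human Lab Sessions 1 and 2 (Table 1). This 14-item self-report rating scale measures alcohol stimulant/ sedative effects". The same two sessions are given for repeated breath alcohol, AUQ, YCS, the video ratings of drinking and in-session vital signs.

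On analysis, 6.4.1 rules out inferential statistics. Section 6.4.3.2 plans descriptive statistics for craving (item 1), alcohol consumption in each session (item 2) and, as item 3, alcohol "medication interaction effects on BAES, DVT, MD gait and body sway check, Alertness VAS and computer tasks (AAT, BART, and DD". Neither blood nor breath alcohol is named in the outcome lists (5.2, 6.2.1) or the analysis lists (6.4.3). On the alcohol itself, 3.3.2 says that "with the exception of the priming dose, they determine the amount of alcohol consumed", and the incentives part of 6.3.5 adds: "At each session, participants are offered 8 drinks".

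**The concern.** **Sessions.** The measure descriptions are where staff would look to see when to draw blood or hand out a scale. Anyone who followed them would skip these measures in Session 3. In a crossover, each man would then lack them under whichever condition he received last. Craving is secondary outcome 1 and BAES is part of secondary outcome 3, so listed outcomes are involved. By-condition summaries would no longer rest on the same men.

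**Interaction.** Section 3.3.2 notes that no lacosamide–alcohol interaction data are published and that added sedation and psychomotor impairment are possible. An interaction outcome asks whether the drug changes the response at a given alcohol level. After the priming drink that level is chosen by the participant, and it may itself respond to lacosamide. If men drink less on the drug, by-dose readings could understate added impairment at a given level; if they drink more, they could overstate it. The plan measures the alcohol level but does not say that it will be shown beside the impairment readings.

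**Working it through.** **1. The session conflict, side by side**

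| Measure | Measure descriptions, 6.3.5 | Elsewhere in the plan |
|---|---|---|
| Blood alcohol | Sessions 1 and 2 | Visit table: 1, 2, 3. Section 3.3.2: draws at all three |
| BAES | Sessions 1 and 2 | Visit table: 1, 2, 3 |
| Breath alcohol | Each visit; repeated in Sessions 1 and 2 | Visit table: 1, 2, 3. Earlier entry in 6.3.5: during each lab session |
| AUQ, YCS | Multiple times in Sessions 1 and 2 | Visit table: 1, 2, 3 |
| Drinking-behaviour ratings | Sessions 1 and 2 | Visit table: 1, 2, 3 |
| In-session vital signs | Sessions 1 and 2 | Visit table: 1, 2, 3. Earlier entry in 6.3.5: several times in each lab session |

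**2. Which reading the plan's own figures support.** Section 3.3.2 gives about 40 cc at intake, about 20 cc at each lab session and a total of 100 ml.

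- Three sessions: 40 + 3 × 20 = 100 ml, the stated total.
- Two sessions: 40 + 2 × 20 = 80 ml, which does not match.

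The venipuncture paragraph counts four draws: 1 screening + 3 lab sessions = 4. The timeline follow-back entry in 6.3.5 names Sessions 1, 2 and 3 and then speaks of two sessions. The AUQ entry refers to a one-month follow-up that the schedule in 6.3.1 does not contain. All this suggests text carried over from another version.

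**3. What would be lost if the two-session wording were followed.** Inputs: 4 completers (5.3.1), 3 sessions each, 3 sequences (6.1.3).

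- Sessions with the measures: 4 × 2 = 8 of 4 × 3 = 12.
- Men with all three conditions: 0 of 4, because each man's third session is a condition he has not had before.

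Those two counts need only four completers. The next two need an assumption, because 6.1.3 does not list the sequences: each condition comes last in exactly one sequence, and the four men are split 2/1/1.

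- Men with data per condition: 4 minus the number who had that condition last, giving 3, 3 and 2 in some order.
- Within-man differences from placebo: 4 × 2 = 8 are possible. A man with placebo last contributes none; any other man contributes one. With one man having placebo last, 4 − 1 = 3 of 8; with two, 4 − 2 = 2 of 8.

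Under the three-session reading the counts are 12 of 12 sessions, 4 men per condition and 8 of 8 differences.

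**4. Which readings mix drug and intake.**

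- Before the priming drink: no alcohol has been given in the session, so nothing is mixed. As 5.1 orders the session, AAT, BART, delay discounting and DVT fall here.
- After the priming drink but before self-administration: the man has not yet chosen any drinks, so the readings are not affected by chosen intake.
- After self-administration begins: intake is chosen and can range from 0 to 8 drinks. Readings of BAES, gait/sway and alertness here carry both influences. Section 3.3.2 confirms that some such readings exist: "Tests of alertness and gait/body sway will be administered throughout the testing day to monitor these effects".

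The only bound on the mixing is a difference of 8 chosen drinks between two sessions of the same man, which is simply the number offered. The documents give no basis for a likely size.

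**The case against.** **On the sessions.** A reader might infer that the trial will lack blood alcohol and BAES in Session 3. The documents do not support that. The visit table, the blood volume, the count of draws and the earlier breath-alcohol and vital-sign entries all say three sessions, so the two-session wording is most likely a remnant. That argument stands against any claim of settled under-collection. It does not make the wording harmless, because it sits in the procedures section and covers two listed secondary outcomes.

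**On the interaction summary.** The case against is strong:

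- Sections 6.4 and 6.4.3 call the listed items the chief variables, and 6.4.3.2 introduces its list as open. The absence of blood and breath alcohol does not mean they will go unreported.
- Drinks consumed per session is item 2, next to the impairment measures in item 3. With four men and no inference, setting one beside the other needs no model.
- The primary aim concerns the "safety of giving lacosamide to human participants in a laboratory alcohol self-administration procedure". Impairment by dose under self-chosen drinking answers that as a total effect. A reader who concludes that the by-dose summaries are invalid, or that the primary safety outcome is compromised, goes further than the text allows.
- Table 1, to which 6.3.5 refers for timing, is not in the text available for review. It may already pair alcohol draws with BAES and gait/sway, and it may repeat some computer tasks after drinking. Neither can be judged.
- A listing would not separate lacosamide's effect from that of chosen intake, since intake follows dosing.

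All of this stands. It reduces the second part to an improvement in display. What remains is that the plan names an interaction outcome, collects the exposure data needed to read it, and does not commit to showing the two together.

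**Conclusion.** The first part holds as an internal conflict: the measure descriptions in 6.3.5 are wrong as written for a three-session crossover. The losses worked out above are conditional on that wording prevailing over the rest of the plan, and the per-condition and difference counts also on the assumed sequences and 2/1/1 split. They are not expected losses.

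The second part holds only as a low-cost improvement for the secondary interaction outcome. Its size cannot be estimated. Time, retention and adverse effects, the primary outcomes, are not affected by it. Overall the point is minor: it limits what the pilot can pass on to later studies, and does not threaten its feasibility and safety aims.

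**What to change.** **Wording in 6.3.5.** Change the measure descriptions to Sessions 1, 2 and 3 for blood alcohol, BAES, repeated breath alcohol, AUQ, YCS, drinking-behaviour ratings and in-session vital signs. Correct the mention of two sessions in the timeline follow-back entry at the same time. If the visit table and the blood-draw text in 3.3.2 are already being followed, this adds no samples or burden. If staff are working from the two-session wording, Session 3 collection of these measures has to be added.

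**Listing in 6.4.3.2.** Add a descriptive listing for each man of BAES, gait/sway and alertness, by condition and by time point (before drinking, after the priming drink, after self-administration), as far as the Table 1 schedule provides them. Show each reading beside the nearest blood or breath alcohol value and the drinks consumed so far, with within-man differences from placebo. State that the listing displays differing intake but does not separate it from lacosamide's effect, and that it cannot rule out an interaction.

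For four completers this is 4 × 3 = 12 man-sessions and at most 12 × 3 = 36 rows. It needs no test, model or extra participant.

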6.4.3.3 Safety

Descriptive statistics will be used to summarize the data. The AE checklist will be used to assess adverse effects. Descriptive statistics will be used.

7. TRIAL ADMINISTRATION

7.1 Institutional Review Board (IRB) Review

[Include a statement about IRB oversight and review throughout the study. This may be institution or sponsor specific.]

7.2 Unanticipated Problems

[Explain how unanticipated problems that may occur during the study will be handled, communicated to the IRB, sponsor, and FDA, if applicable.]

7.3 Study Monitoring

[Specify who will monitor the study (third party, sponsor, internal team, etc.), where monitoring will occur and frequency. Describe any related responsibilities and identify anyone who will review the study for accuracy and how often.]
Study monitoring will be conducted by the DSMB.

7.4 Data Safety Monitoring Plan

Plan to monitor study progress and safety: The Data and Safety Monitoring Plan (DSMB)

The DSMP for this project consists of:

- a Data and Safety Monitoring Board (DSMB)
- a schedule of DSMB meetings to review study data and events
- a list of study data and event items to be reviewed by the DSMB
- procedures for communicating DSMB findings to the CHR, the study sponsor (Department of Defense) and other appropriate entities

- a plan for conducting and reporting interim analysis
- stopping rules
- rules for withdrawing study participants from the study interventions

These elements of the DSMP are described below:

The Data and Safety Monitoring Board (DSMB)

The Data and Safety Monitoring Board (DSMB) is a group of 3 physicians who are not study investigators and who are experts in the area of clinical research and substance use disorders. The current composition of the PI's DSMB is: [name]., a clinical investigator and Medical Director, PTSD Clinic, SFVAMC; [name]. [medical Monitor], an experienced human clinical investigator, Assistant Professor of Psychiatry at University of California, San Francisco and [name]., Ph.D., an experienced basic neuroscience investigator and attending psychiatrist, SFVAMC.

The DSMB will meet biannually to review data reports prepared by the PI regarding the progress of the study and will monitor patient enrollment, retention, outcomes, adverse events, and other issues related to patient safety. The DSMB will make recommendations to the PI as to whether the study should continue or be modified or terminated. The DSMB can consider patient safety or other circumstances as grounds for early termination. Any member of the DSMB can ask for a meeting of the group if he/she feels that it is necessary, based upon the data.

During the course of the study, reports will be prepared and distributed to the Data and Safety Monitoring Board on a biannual basis. In order for the Data and Safety Monitoring Board to discharge their duties for overseeing the study and the rights of the patients, they will receive analyses of the primary outcome measures and the important secondary measures on a quarterly basis. The DSMB will receive reports of serious adverse events (SAEs) within 72 hours of their occurrence.

DSMB Minutes will be prepared by the Study Coordinator within 5 working days after each biannual DSMB meeting.

Medical Monitor

[name]., Medical Director of the PTSD Clinic at San Francisco VA Medical Center will serve as the Medical Monitor. As Medical Monitor, [name] will review all unanticipated problems involving risk to subjects or others, serious adverse events and all subject deaths associated with the protocol and provide an unbiased written report of the event. At a minimum, the medical monitor will comment on the outcomes of the event of problem and in case of a serious adverse event or death, comment on the relationship to participation in the study. The Medical Monitor will also indicate whether she concurs with the details of the report provided by the principal investigator. Reports for events determined by either the investigator or medical monitor to be possibly or definitely related to participation and reports of events resulting in death will be promptly forwarded to the IRB and other governing authorities.

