5.3.1 Number of Participants

The study will enroll 4 men participants. We anticipate needing to start up to 6 participants to get 4 to complete all 3 human lab sessions.

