6.3.1 Study Schedule

STUDY VISIT	WEEK	TYPE OF VISIT	AMOUNT OF TIME
1	1	Baseline/screening	3 hours
2	2	Human lab session 1	12 hours
		Phone visit 1	10 minutes
	3	WASHOUT	
3	4	Human lab session 2	12 hours
		Phone visit 2	10 minutes
	5	WASHOUT	
4	6	Human lab session 3	12 hours
		Phone visit 3	10 minutes
5	7	Follow-up visit	1 hour
TOTAL		5 visits	40 hours and 30 minutes

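### Section 7.4 ties DSMB review to the calendar at two unreconciled frequencies, so in a study of 4 to 6 men the scheduled review may come after most or all dosing

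*Combined protocol and SAP*

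**What the plan says.** Section 7.4 (Data Safety Monitoring Plan) sets these frequencies:

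- Meetings: "The DSMB will meet biannually to review data reports prepared by the PI regarding the progress of the study". The same paragraph has the board advise on whether the study continues, changes or ends.
- Reports: "reports will be prepared and distributed to the Data and Safety Monitoring Board on a biannual basis".
- Analyses, in the next sentence: "they will receive analyses of the primary outcome measures and the important secondary measures on a quarterly basis".
- Minutes are tied to the twice-yearly meeting only.
- Outside the cycle: "The DSMB will receive reports of serious adverse events (SAEs) within 72 hours of their occurrence", and "Any member of the DSMB can ask for a meeting of the group if he/she feels that it is necessary", based on the data.

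The section also lists an interim-analysis plan among the elements it will describe, but none follows.

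On scale and timing, Section 5.3.1 states: "We anticipate needing to start up to 6 participants to get 4 to complete all 3 human lab sessions". The table in Section 6.3.1 puts sessions 1, 2 and 3 in weeks 2, 4 and 6 ("Human lab session 3" is the week 6 row) and follow-up in week 7. Section 5.1.1 allows sessions as little as 7 days apart.

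On why monitoring matters, Section 3.3.2 says: "There are no published reports of lacosamide-alcohol pharmacokinetic (PK) or pharmacodynamics interactions". It goes on to expect possible added sedation and psychomotor impairment. Adverse effects are a primary outcome (5.2.1). Alertness, gait and body sway are secondary outcomes (5.2.2).

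**The concern.** Two frequencies appear in adjacent sentences with no statement of how they fit together. A reader cannot tell whether a quarterly analysis prompts a board review or only goes on file until the next twice-yearly meeting. Nor is either clock tied to the first dosing.

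The larger issue is the mismatch between calendar rules and a very small, short study. A man's exposure runs from his first session to his third: 4 weeks by the schedule table, 2 weeks at the minimum spacing in Section 5.1.1. It can fall entirely between two reviews at either frequency, whatever the recruitment pace. Yet Section 3.3.2 gives the board a say in withdrawing a man for events between his sessions, and Section 7.3 assigns study monitoring to the board. If the only scheduled decision point comes when dosing is nearly over, the board's advice on continuing or modifying has little left to act on. The study's aims include establishing safety and refining the procedures (4.2), and a late review serves neither well.

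**Working it through.** **Inputs**

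- Session weeks 2, 4 and 6 per man (6.3.1). As a check on the table, 3 h + 3 × 12 h + 3 × 10 min + 1 h = 40.5 h, which matches its stated total of 40 hours and 30 minutes.
- 3 sessions per man (5.1): 4 × 3 = 12 sessions, or at most 6 × 3 = 18 if six men start and all attend every session.
- Review intervals (7.4), read as 26 weeks for biannual and 13 weeks for quarterly.
- **Assumed, not in the documents:** the gap g in weeks between successive starts, and a review clock that begins at the first man's week 1. Recruitment time is itself a primary outcome (5.2.1), so g is unknown and is varied below.

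**Formula**

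Man i has sessions in weeks g(i − 1) + 2, g(i − 1) + 4 and g(i − 1) + 6. Count those at or before the review week R. For 4 men the last session is in week 3g + 6. All 12 are therefore done by week 26 if 3g + 6 ≤ 26, so g ≤ 6 whole weeks. All 12 are done by week 13 if 3g + 6 ≤ 13, so g ≤ 2 whole weeks.

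**Back-to-back example (g = 7, 4 men)**

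Sessions fall in weeks 2, 4, 6; 9, 11, 13; 16, 18, 20; 23, 25, 27. By week 26, 11 of 12 are done. By week 13, 6 of 12 are done (5 if a session in the review week itself is not counted).

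**Range for 4 men, table schedule**

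| Gap between starts (weeks) | Done by week 13 | Done by week 26 |
|---|---|---|
| 2 or less | 12 of 12 | 12 of 12 |
| 4 | 8 | 12 |
| 6 | 6 | 12 |
| 7 | 5 or 6 | 11 |
| 8 | 5 | 9 or 10 |
| 13 | 3 | 6 |
| 26 | 3 | 3 |

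Two values in a cell mean that one session falls in the review week itself.

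**Variations**

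- *Six starters, all attending.* Back to back, 11 of 18 are done by week 26. With starts 4 weeks apart, the last session is in week 5 × 4 + 6 = 26, so 17 or 18 of 18 are done.
- *Minimum 7-day spacing (weeks 2, 3, 4), 4 men.* The last session is in week 3g + 4, so 12 of 12 are done by week 26 at gaps up to 7 weeks, and 9 or 10 at 8 weeks.
- *Unanchored clock.* Section 7.4 describes the current membership of the investigator's board, so its meeting dates may not follow this study's first dosing. In the back-to-back case the count at the first meeting could then be anything from 0 (week 1) to 11 (week 26).

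**The case against.** The strongest reply has three parts.

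First, the two frequencies are compatible. Meetings, reports and minutes twice a year, with analyses sent every quarter, can be two separate deliverables. A reader might infer a contradiction, but the text does not establish one. It leaves an ambiguity about how the two connect.

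Second, a reader might infer from the 7-week schedule alone that 11 or 12 of 12 sessions will be over before the first review. The documents do not support this. The count also needs the gap between starts and the date of the first review, and neither is given. One extra week between starts lowers 11 to 9 or 10.

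Third, the board is not blind between meetings. It gets serious adverse events within 72 hours, and the quarterly analyses cover adverse effects. The investigator is to report the relatedness of each adverse event to it (6.2.2.1). Any member can ask for a meeting on the data, without restriction to serious events. The board or the investigator can stop the study on judgment (6.3.6), and a study-related serious adverse effect halts it (7.5). The study physician reviews safety at each visit, and the team meets weekly (6.2.2.1).

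All three parts stand as limits on the point. They do not remove it. The per-event reports to the board have no stated timing or decision step. The quarterly analyses have no stated review attached, and they include only those secondary measures judged important. An ad hoc meeting depends on someone asking. The physician's review and the weekly meetings belong to the study team and are not independent. None of these is a scheduled independent review of accumulating non-serious adverse-effect, alertness and gait data while men are still being dosed.

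**Conclusion.** The point holds in a conditional form. Section 7.4 leaves the relation between its two frequencies, and the timing of the first review, unstated. Under prompt enrolment its only scheduled continue, modify or stop review can follow most or all dosing. For 4 men and a review 26 weeks after the first man's week 1, that means 11 or 12 of 12 sessions at gaps of 7 weeks or less. Slower recruitment eases it: 9 or 10 at 8 weeks, 6 at 13 weeks and 3 at 26 weeks.

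A reader might go further and conclude that the board's review cannot change anything for these men. That does not follow. In the back-to-back case about half the sessions remain at week 13 and one remains after week 26, and the board can act outside its schedule. The gap concerns scheduled review of non-serious data, not oversight of serious events. It should be corrected, but the existing serious-event safeguards keep it from being critical.

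**What to change.** Rewrite the frequency paragraph of Section 7.4 so that it:

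1. states one cadence for meetings, reports, analyses and minutes, replacing the two now given;
2. ties the first reviews to participant count: adverse-effect, alertness/gait and retention data go to the board after the first man completes or stops his sessions, and again after the second;
3. sets reviews at least quarterly after that.

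Whether new starts wait for the first two reviews should be left to the sponsor and the board, and the choice recorded. A wait would lengthen the time to recruit and run 4 participants, which is a primary outcome, so it should be reported alongside that figure.

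The cost is one paragraph and one or two extra short reports, on one or two men, to an existing board.
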